13.4 Definitions of Failure

The following table shows how each first event will be counted for progression-free survival, local-regional failure, and distant metastasis. Anything not explicitly in the table (e.g., second primary tumor) is not considered an event, and the patient will continue to be followed for failure. For overall survival, death from any cause will be considered a failure. All failure times will be measured from randomization to the date of failure, competing risk, or last follow-up.

First event	Progression-Free Survival	Local-Regional Failure	Distant Metastasis
None	Censored	Censored	Censored
Local-regional progression or recurrence	Failure	Failure	Competing risk
Distant metastasis	Failure	Competing risk	Failure
Death due to study cancer or from unknown causes	Failure	Failure	Competing risk
Death to due any other reason	Failure	Competing risk	Competing risk
Salvage surgery of primary with tumor present/unknown	Failure	Failure	Competing risk
Salvage neck dissection with tumor present/unknown, > 20 weeks from end of RT	Failure	Failure	Competing risk

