13.5 Sample Size and Patient Accrual (9/27/16)

This study will be a randomized phase II screening trial as proposed by Rubinstein, et al (2005). Based on the accrual to RTOG 0129 in this population, it is expected that the monthly accrual will be 12 patients after the first 6 months post-activation (allowing for IRB approvals). In RTOG 0129, this group of patients treated on the accelerated fractionation arm had a 2-year progression-free survival (PFS) rate of 53.5%. Hazard rates for first and second years are 37% and 15%. Based on discussions with the study chair, a 35% reduction in the hazard rate is clinically meaningful. With statistical power 0.80 and significance level 0.20 (1-sided) and one interim efficacy and futility analysis, the Lan-Demets (OF) spending function boundary for efficacy and rho family spending function with parameter of 1.5 for futility were utilized to derive a nonbinding rule. A total of 69 PFS events are required. To observe the required number of events, a sample size of 158 accrued over 1.22 years with an additional 2.6 years of follow-up (total study duration 4.3 years including 6 months for IRB approvals) is required. Allowing for up to 10% of patients to be ineligible or not evaluable, **the total original required sample size is 176.**

Following activation of the study little accrual is anticipated initially. The date at which the first patient is accrued will be used as the baseline for monitoring accrual. If the total accrual during months 18 through 24 is less than 20% of the projected total for 6 months of accrual (15 patients), then the study statistician will recommend to the RTOG DMC and the sponsor that the protocol will be discontinued. If the total accrual is between 21-49%, then the protocol will continue to accrue subjects pending approval to remain open by the RTOG DMC and the study sponsor.

Revised Sample Size and Patient Accrual

As of September 2016, the observed accrual rate in this study is about 30 patients/year (2.5/month). To finish accrual within a reasonable timeframe and to maintain the same design parameters detailed above, we plan to accrue a total of 142 patients (128 analyzable), with a total accrual duration of 4.7 years instead of 5.9 years. According to this plan, we will finish accrual around March 2017.

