13.6 Analysis Plan (9/27/16)

Progression-free and overall survival rates will be estimated using the Kaplan-Meier method (1958) and rates of distant metastasis (DM) and local-regional control (LRC) by the cumulative incidence method (Kalbfleisch 1980) to account for competing risks (see Section 13.4). The distributions of the progression-free and overall survival times will be compared between treatment arms with a one sided log rank test (Mantel, 1966). Distant metastasis and local-regional control will be compared using cause-specific log rank test. If the resulting p-value for PFS is < 0.1803 , the result will be interpreted as a significant indication of lapatinib improving progression-free survival of these patients to warrant a definitive phase III trial.

Only adverse events (AEs) assessed to be definitely, probably, or possibly related (if the relationship is missing, it will be assumed to be definitely, probably, or possibly) to protocol treatment will be considered. The rates of adverse events and treatment compliance will be estimated using a binomial distribution along with their associated 95% confidence intervals and will be compared using Fisher's exact test.

Comparison of change from baseline quality of life scores between the 2 arms will be done using a 2-sample independent t test. With 158 patients, we will have 87% power to detect an effect size of 0.5 with a two-sided type I error rate of 5% and the statistical power will be 79% and 66% to detect effect sizes of 0.5 with 126 and 94 patients. Analysis of the covariance model (ANCOVA) will be used to adjust for effects from other factors.

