For analysis of local-regional control, distant metastasis, PFS, and OS, we will examine whether patients with normal baseline levels of biomarkers have a different prognosis than patients with abnormal baseline levels by calculating the product-limit estimates of the survival function and comparing those estimates using the log-rank statistic. The relationship between local-regional control, distant metastasis, PFS, OS, and abnormal baseline marker levels also will be explored by fitting Cox proportional hazards regression models, both adjusted for baseline disease and patient characteristics and unadjusted. Assuming usable baseline tissue/blood samples can be obtained from 118 eligible patients (~75%), this will provide at least modest power (>69%) to detect large differences (hazard ratios > 2.0) between patients with normal and abnormal marker levels, assuming 50% abnormal prevalence, with a two-sided 5% alpha, for the PFS endpoint.

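### Section 13.6 names product-limit estimates for local-regional control and distant metastasis by marker group, against its own cumulative-incidence rule; if competing first events are censored, those failure rates are overstated

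*Combined protocol and SAP*

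**What the plan says.** Three places in the combined protocol and SAP bear on this.

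- **Section 13.4 (Definitions of Failure)** uses first-event coding: "The following table shows how each first event will be counted for progression-free survival, local-regional failure, and distant metastasis". Distant metastasis and death from other causes compete with local-regional failure. Deaths from the study cancer or of unknown cause count as local-regional failures. For distant metastasis, every death, every local-regional failure and the listed salvage operations are competing events.
- **Section 13.6, opening paragraph**, uses Kaplan-Meier for PFS and OS. Rates of the other two endpoints are estimated "by the cumulative incidence method (Kalbfleisch 1980) to account for competing risks (see Section 13.4". The test is also named: "Distant metastasis and local-regional control will be compared using cause-specific log rank test".
- **Section 13.6, biomarker paragraph**, takes all four endpoints together: "For analysis of local-regional control, distant metastasis, PFS, and OS, we will examine whether patients with normal baseline levels of biomarkers" differ in prognosis from those with abnormal levels, by "calculating the product-limit estimates of the survival function and comparing those estimates using the log-rank statistic". The relationship "also will be explored by fitting Cox proportional hazards regression models, both adjusted for baseline disease and patient characteristics and unadjusted". No exception is made for the two endpoints with competing events.

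**The concern.** Two paragraphs of one section name different estimators for the same two endpoints, and nothing explains why competing events matter in one place and not in the other. A product-limit curve has no state for a competing event, so its natural use here censors such events. One minus that curve then estimates the failure probability in a setting where the competing events could not happen, and it is at least as large as the proportion of patients who actually fail from that cause.

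What is at stake is description. Rates and curves by marker group would be too high, and unevenly so if one group has more first events. Distant metastasis has the longest list of competing events, and it is the endpoint of a named aim, the validation of LOX and Gli1 (Section 1.6.5).

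**Working it through.** **Inputs from the documents.** Section 13.5 says that comparable patients on the accelerated-fractionation arm of RTOG 0129 "had a 2-year progression-free survival (PFS) rate of 53.5"%. The yearly rates given there, 37% and 15%, reproduce this when read as conditional failure probabilities: 0.63 × 0.85 = 0.5355. So event-free survival S at 2 years is 0.535, and 46.5% have had a first event. The biomarker paragraph assumes 118 patients, 50% abnormal prevalence and a hazard ratio of 2.0.

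**Input not in the documents.** The share s of first events due to a given cause is not stated. I assume it is constant over time and vary it from 20% to 70%.

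**The plan's own figure.** The stated biomarker power (above 69%) reproduces. Events = 69 × 118/158 = 51.5, and √(51.5 × 0.25) × ln 2 − 1.96 = 0.53, which gives power 0.70. That figure is for PFS and does not depend on the disputed estimator.

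**Formulas**, with proportional cause-specific hazards:

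- cumulative incidence = s × (1 − S)
- one minus product-limit, with competing events censored = 1 − S^s

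**Results at 2 years, S = 0.535:**

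| Share s | Cumulative incidence | 1 − product-limit | Excess (points) |
|---|---|---|---|
| 20% | 9.3% | 11.8% | 2.5 |
| 25% | 11.6% | 14.5% | 2.9 |
| 30% | 13.9% | 17.1% | 3.2 |
| 50% | 23.2% | 26.9% | 3.6 |
| 60% | 27.9% | 31.3% | 3.4 |
| 70% | 32.5% | 35.5% | 2.9 |

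In relative terms the excess runs from 26% (s = 20%) down to 9% (s = 70%). A simulation of 200,000 patients agreed with the formulas: 27.9% against 31.3% for s = 60%, and 11.7% against 14.5% for s = 25%.

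**Two marker groups.** Take equal groups with an all-cause hazard ratio of 2 whose average S is 0.535. With x the better group's event-free survival, 0.5x + 0.5x² = 0.535, so x = 0.649 and x² = 0.421. For shares of 20% to 70%, the same in both groups:

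- better-prognosis group (S = 64.9%): excess 1.3 to 1.9 points
- worse-prognosis group (S = 42.1%): excess 4.3 to 6.2 points

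At s = 50%, cumulative incidence is 17.6% and 28.9%, against 19.4% and 35.1% from the product-limit. The displayed difference grows from about 11 to about 16 points.

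**The case against.** **The opening paragraph may be the general rule.** Its sentence on estimating rates is not restricted to the treatment arms; the arms enter only in the following sentence, on testing. One could then read the biomarker paragraph as describing only how prognosis is compared, with cumulative incidence still governing any reported rate. This is a fair reading, and it makes the defect one of drafting. But the biomarker paragraph names an estimator for these endpoints, so an analyst following it literally would produce the wrong curves.

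**Censoring is not stated.** This is true. It is the natural use of the method, but the overstatement is conditional on it.

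**The excess is small against sampling error.** With 118/2 = 59 patients per group, the standard error of a 27.9% rate is √(0.279 × 0.721/59), or about 5.8 points. The 2-year excess of 2.5 to 3.6 points is smaller. This limits the practical weight, although a systematic excess does not average out.

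**Marker-group rates need not match overall rates anyway.** Only patients with usable samples contribute, so some disagreement is expected under either estimator. I place no weight on that disagreement.

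**Stronger readings that the documents do not support.**

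- A reader might infer that the biomarker tests are invalid. A log-rank test or Cox model that censors competing events is a cause-specific comparison, which is what the opening paragraph of Section 13.6 specifies.
- A reader might put the distortion down to competing deaths alone. All competing first events contribute, and for local-regional failure the deaths from cancer or unknown cause are failures, not competing events.
- A reader might quote much larger 5-year gaps. Section 13.5 gives rates for years 1 and 2 only, so any 5-year figure is an extrapolation and not the plan's own.

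**Conclusion.** The inconsistency within Section 13.6 is real. If competing first events are censored, the direction of the error is certain whatever the cause shares: one minus the product-limit estimate is never below cumulative incidence, and it is above it once a competing event precedes an event of interest. The sizes in the table, and the uneven excess between marker groups, rest on the assumed constant shares; the group figures also rest on the hazard-ratio-2 illustration.

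The defect is confined to the estimated rates and curves for two endpoints by marker group. PFS and OS have no competing events under Section 13.4. The biomarker objective is exploratory (Section 2.2.6), and the phase III decision rests on the PFS comparison. This is a minor point, worth correcting because the correction is so cheap.

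**What to change.** Amend the biomarker paragraph of Section 13.6 to say three things:

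1. Local-regional control and distant metastasis are estimated by marker group with cumulative incidence, using the first-event coding of Section 13.4.
2. Product-limit estimates are kept for PFS and OS.
3. The log-rank tests and Cox models for local-regional control and distant metastasis are cause-specific, with competing first events censored at the time they occur.

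The cost is a sentence or two. No new data are needed, the event coding already exists, and sample size and the stated PFS power do not change.

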13.6.1 Interim Analysis to Monitor Study Progress

Interim reports will be prepared twice each year until the final analysis has been accepted for presentation or publication. In general, these reports will contain information about the accrual rate with projected completion date for the accrual phase, exclusion rates and reasons, pretreatment characteristics of patients accrued, compliance rate of treatment delivered with respect to the protocol prescription, and the frequency and severity of AEs. The RTOG Data Monitoring Committee (DMC) will review this study twice a year in conjunction with the RTOG semiannual meetings with respect to patient accrual and morbidity. The DMC also will review this study on an "as needed" basis between meetings.

13.6.2 Significance Testing for Early Termination and Reporting

One interim treatment comparison will be performed when 50% (34 PFS failures) of the 69 required number of PFS failures are observed. Only the primary endpoint will be tested in the interim analysis. The efficacy will be tested using boundary of 0.0699 on the p value scale for the interim tests and 0.1803 for the final analysis to preserve an overall alpha level of 0.20 for the study. A single interim futility analysis will be conducted when one-half (34) of the requisite events for definitive analysis have been observed. If the p value is equal to or greater than 0.5827 favoring the control (i.e. in the wrong direction with respect to demonstrating that the lapatinib arm is more favorable), then early stopping will be considered. The results will be reported to the RTOG DMC with the treatment blinded. The responsible statistician may recommend early reporting of the results and/or stopping accrual (if applicable) of the trial if the treatment effect with respect to PFS is highly significant or if it is not likely to be.

13.6.3 Analysis for Reporting the Initial Treatment Results

The analysis to report the initial results of treatment will be undertaken when each patient has finished concurrent therapy, around July 2017. All randomized patients (ITT) will be included in the analysis. Eligible patients with both on-study and follow-up information will be considered for sensitivity analysis. The emphasis of this analysis will be on treatment compliance and adverse events. The usual components of this analysis are:

- Tabulation of all cases entered, and any excluded from analysis with reasons for exclusion;
- Patient accrual rate;
- Institutional accrual;
- Distribution of important baseline prognostic variables;
- Frequency and severity of adverse events;
- Compliance rate for treatment delivery with respect to the protocol prescription;
- Observed results with respect to the endpoints described above.

Only adverse events (AEs) assessed to be definitely, probably, or possibly related (if the relationship is missing, it will be assumed to be definitely, probably, or possibly) to protocol treatment will be considered. The rates of adverse events, treatment compliance, will be estimated using a binomial distribution along with their associated 95% confidence intervals and will be compared using Fisher's exact test.

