7.0 DRUG THERAPY

Institutional participation in chemotherapy studies must be in accordance with the Medical Oncology Quality Control guidelines stated in the RTOG Procedures Manual.

Protocol treatment must begin within 14 calendar days after randomization.

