13.6.4 Analysis for Reporting the Final Treatment Results

The analysis to report the definitive results of treatment will be undertaken when 69 events (total from both arms) have been reported for the primary endpoint, PFS, unless the criteria for early stopping are met. The time from when accrual is finished to this analysis is projected to be approximately 2.7 years based on the observed accrual rate. All randomized patients (ITT) will be included in this analysis. Eligible patients with both on-study and follow-up information will be considered for sensitivity analysis. The usual components of this analysis are:

- Tabulation of all cases entered, and any excluded from analysis with reasons for exclusion;
- Patient accrual rate;
- Institutional accrual;
- Distribution of important baseline prognostic variables;
- Frequency and severity of adverse events;
- Observed results with respect to the endpoints described above.

The difference in PFS between the control arm and the experimental arm will be tested using the one sided log-rank statistic at the significance level of 0.1803 given that the one interim analysis is carried out and shows no statistical significance. If the resulting p-value for efficacy is <0.1803, this result will be interpreted as an indication of lapatinib in improving progression-free survival in these patients.

A final analysis report will be prepared and provided for review by the co-investigators. Results for dissemination will be developed, and a manuscript drafted for review, approval, and submission. After manuscript acceptance, patient follow up will be discontinued and the trial terminated. It is anticipated that termination will occur approximately 3.9 years from when the accrual is finished. This time-frame may be extended depending on factors such as the observed accrual and event rates, in which case a new trial termination date will be established.

REFERENCES

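### Adverse-event rates fall under the all-randomized set and no treated-patient set is defined, so any patient who never starts treatment dilutes the reported toxicity, probably by a small amount

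*Combined protocol and SAP*

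**What the plan says.** Section 13.6.3 sets the population for the initial report: "All randomized patients (ITT) will be included in the analysis". It then gives the purpose of that report: "The emphasis of this analysis will be on treatment compliance and adverse events". The numerator is restricted: "Only adverse events (AEs) assessed to be definitely, probably, or possibly related" to protocol treatment are considered, and a missing attribution is taken as related. The estimator follows: "The rates of adverse events, treatment compliance, will be estimated using a binomial distribution along with their associated 95% confidence intervals", with Fisher's exact test between arms. Section 13.6 gives the same estimator and names no denominator. Section 13.6.4 covers the final report, which lists frequency and severity of adverse events among its components, and says "All randomized patients (ITT) will be included in this analysis".

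The only other set in 13.6.3 and 13.6.4 is a sensitivity set: "Eligible patients with both on-study and follow-up information will be considered for sensitivity analysis". Eligibility and available data define it; receipt of treatment does not. Section 7.0 allows a gap before the first dose: "Protocol treatment must begin within 14 calendar days after randomization".

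**The concern.** All randomized patients is the right set for PFS, OS and compliance. For treatment-related toxicity it makes the numerator and denominator describe different populations. A patient who withdraws or deteriorates between randomization and the first dose has no treatment to which an event could properly be attributed, yet counts as one patient without toxicity. Such patients can occur. Treatment may start up to 14 days after randomization, and section 7.4.8 provides no starter supply, so study drug ships only after randomization. The sensitivity set does not help, because an eligible non-starter who is followed remains in it.

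Toxicity and tolerability are a secondary objective (2.2.3), and section 1.2 says the results bear on the design of a later phase III trial. The error would always lower the reported rates, in both arms.

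**Working it through.** **Inputs from the documents**
- Accrual target 142, of whom 128 analyzable; allowance of up to 10% for patients ineligible or not evaluable (13.5).
- Two arms (13.3). The ratio is not stated; I assume 1:1, so 71 per arm.
- Illustrative rates p: about two thirds for grade 3-4 mucositis and/or dysphagia (6.9), and 15% for grade 3 diarrhea on lapatinib monotherapy (7.4.6.4). I add p = 40% as an intermediate value of my own.

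**Input not in the documents**
- u, the share randomized but never treated. I assume 0 to 5%.

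**The plan's own figures.** The plan states no adverse-event rate or power for this trial. The figures nearest to the question are the accrual totals: 158/0.9 = 175.6, rounded up to 176 as stated; 142 x 0.9 = 127.8, or about 128 as stated.

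**Dilution.** If non-starters contribute no related event, reported rate = p x (1-u), and the understatement is p x u.

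| p | u = 0 | u = 2% | u = 3% | u = 5% |
|---|---|---|---|---|
| 66.7% | 66.7% | 65.3% | 64.7% | 63.3% |
| 15% | 15.0% | 14.7% | 14.55% | 14.25% |

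At u = 5% the understatement is 66.7 x 0.05 = 3.3 points and 15 x 0.05 = 0.75 points. The standard error of one arm's rate, sqrt(p(1-p)/71), is 5.6 points for two thirds and 4.2 points for 15%, so the shift is well inside sampling error.

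**Worked example.** With 71 in an arm and 4 never treated (5.6%), 45 events give 45/67 = 67.2% (exact 95% CI 54.6 to 78.2) among treated patients, against 45/71 = 63.4% (51.1 to 74.5) among all randomized.

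**Difference between arms.** With equal u, p1(1-u) - p2(1-u) = (p1 - p2)(1-u). A true 10-point difference is reported as 9.5 points at u = 5%.

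**Coverage of the exact 95% interval** for the on-treatment rate, n = 71, summed over Binomial(71, p(1-u)):

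| p | u = 0 | u = 3% | u = 5% |
|---|---|---|---|
| 15% | 97.1% | 97.2% | 97.1% |
| 40% | 97.2% | 96.9% | 96.3% |
| 66.7% | 96.8% | 95.9% | 93.9% |

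Of the six cells with u above zero, one falls below 95%, and only by about one point.

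**The case against.** The strongest reply is that the denominator is inferred. The all-randomized sentence covers each report as a whole, the sentences on adverse-event rates name no denominator, and both reports also list cases excluded from analysis with reasons. That is fair as far as it goes. But no exclusion rule for adverse events is given, and the only primary set stated for these reports is all randomized patients. An analyst following the text would use it.

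The second reply is that little depends on the answer. The decision to proceed to phase III is the PFS p-value, and no stopping rule uses an adverse-event rate. Blinding makes it unlikely that non-starting differs by arm, so Fisher's test should keep its type I error. Compliance appears in the same initial report and would help expose non-starters. This stands, and it limits the weight of the point.

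Three stronger readings are tempting, and the documents do not support them.

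- A reader might take the 10% allowance in 13.5 as the never-treated share. That would put the two-thirds rate at 60.0%, with coverage of 83.9%. The allowance is for ineligible or not evaluable patients, and a patient found ineligible may have been fully treated. Even at 10%, coverage for a 15% rate is 96.5%.
- A reader might infer that patients given the other arm's tablets would be misclassified. Supplies are blinded, patient-specific and labelled with patient ID and initials (7.4.7), and they are sent after central randomization (7.4.8). Nothing suggests that this is a realistic problem.
- A reader might say that an untreated patient can never contribute an event. Because a missing attribution counts as related, an unattributed event could be counted. The accurate statement is that such a patient essentially cannot contribute one.

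The illustrative rates also have limits. The 15% comes from monotherapy. The two-thirds figure is radiation toxicity enhanced by cisplatin, which a patient who takes no study tablets but receives chemoradiation can still have. For that rate, never treated has to mean no protocol treatment of any kind.

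**Conclusion.** The point holds in a modest form. As written, treatment-related adverse-event rates fall under an all-randomized denominator and no treated-patient set exists to replace it, so any non-starters lower the reported rates in both arms. The direction is clear if anyone fails to start. The size rests on an assumed u of 0 to 5%: 0 to 3.3 points on a two-thirds rate and 0 to 0.75 points on a 15% rate, with little loss of coverage. If every randomized patient starts treatment, the bias is zero. The documents do not support a claim of serious understatement, or of a distorted test between arms. This is a cheap improvement to the wording and does not affect the primary analysis.

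**What to change.** In 13.6, 13.6.3 and 13.6.4, state that adverse-event rates, their confidence intervals and the Fisher comparisons use randomized patients who received at least one dose or fraction of any protocol treatment. Group them by lapatinib or placebo actually received, or by assigned arm if neither was taken; without that last clause, a patient who had chemoradiation but no study tablets would belong to no group. Show the number never treated by arm. Keep all randomized patients for PFS, OS, local-regional control, distant metastasis and compliance.

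The cost is one sentence in each section and no new data. Reported toxicity rates may become slightly less favourable, and the adverse-event denominator slightly smaller.

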6.9 Radiation Therapy Adverse Events

Grade 3-4 (CTCAE, v. 4) therapy-induced mucositis and/or dysphagia, which are enhanced by cisplatin, are expected to develop in about two thirds of patients. Other common radiation adverse events include: fatigue, weight loss, regional alopecia, xerostomia, hoarseness, transient ear discomfort, dysgeusia, and skin erythema and desquamation within the treatment fields.

Less common long-term treatment adverse events include: hypothyroidism, loss of hearing, and chronic swallowing dysfunction requiring permanent feeding tube, and cervical fibrosis. Much less common radiation adverse events include: mandibular osteoradionecrosis (< 5% incidence with attention to the dental recommendations provided in Appendix VII), and cervical myelopathy (<1% with restriction of spinal cord dose to \leq 45 Gy).

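### Adverse-event rates are crude binomial proportions with no stated time horizon, although follow-up at the July 2017 report runs from about 4 months to 5 years

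*Combined protocol and SAP*

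**What the plan says.** Section 13.6.3 sets the method for the initial report: "The rates of adverse events, treatment compliance, will be estimated using a binomial distribution", with 95% confidence intervals and Fisher's exact test. Section 13.6 has the same sentence for the trial as a whole ("The rates of adverse events and treatment compliance will be estimated using a binomial distribution"), so it also governs the final analysis.

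On timing, Section 13.6.3 states: "The analysis to report the initial results of treatment will be undertaken when each patient has finished concurrent therapy, around July 2017". On purpose: "The emphasis of this analysis will be on treatment compliance and adverse events". On population: "All randomized patients (ITT) will be included in the analysis".

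The revised plan in Section 13.5 is to enrol 142 patients at about 30 per year, "with a total accrual duration of 4.7 years instead of 5.9 years", finishing around March 2017.

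Adverse events are evaluated weekly on treatment and then at every scheduled follow-up column of Appendix I, including the one for year 2 onward. Section 6.9 expects late effects: "Less common long-term treatment adverse events include: hypothyroidism, loss of hearing, and chronic swallowing dysfunction", among others, but gives no frequency for this group. Toxicity and tolerability are a secondary objective (Section 2.2.3).

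For distant metastasis and local-regional control, Section 13.6 already specifies cumulative incidence with competing risks and a cause-specific log-rank test. Neither is extended to adverse events.

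**The concern.** A binomial proportion is easy to interpret when every patient has had the same opportunity to show the event. That is true of acute toxicity once treatment is complete. It is not true of events that appear months or years after radiotherapy. In July 2017 the denominator will mix patients entered about five years earlier with patients entered about four months earlier. The late-event percentage will then be an average over that mixture. It is not the risk at 1, 2 or 5 years, and its confidence interval describes sampling error around a quantity that would change if the same patients had been enrolled at a different pace.

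What is at stake is modest. Readers weighing a phase III trial, or comparing this regimen with others, will want late swallowing, hearing and thyroid toxicity tied to a stated time. The primary progression-free survival (PFS) decision does not depend on it.

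**Working it through.** **Spread of follow-up.** Inputs from Section 13.5: 142 patients, 30 per year, accrual ending about March 2017. Check of the plan's own figures: 142/30 = 4.73 years and 176/30 = 5.87 years, matching the stated 4.7 and 5.9. A cut in July 2017 is about 4 months (0.33 years) after the last entry, so potential follow-up e runs from 0.33 to 0.33 + 4.7 = 5.03 years, with a midpoint of about 2.7. Assuming uniform accrual:

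- under 1 year: (1 − 0.33)/4.7 ≈ 14%, about 20 of 142 patients;
- under 2 years: (2 − 0.33)/4.7 ≈ 35%, about 50 of 142 patients.

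**Patients still on maintenance.** One week of lead-in, 6 weeks of radiotherapy and 3 months of maintenance make about 4.6 months, or 5.1 with the permitted 14 days before starting. At 2.5 patients per month, up to about 2.5 × (5.1 − 4) ≈ 3 patients are still on study drug if the cut is 4 months after the last entry, and about 2.5 × (5.1 − 3) ≈ 5 if it is 3 months.

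**What the crude proportion estimates.** Assume a constant late-event hazard λ and no deaths, so F(t) = 1 − exp(−λt). The plan counts any event seen so far, so the expected crude proportion is the mean of F(e) over e uniform on (a, b):

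crude = 1 − [exp(−λa) − exp(−λb)] / [λ(b − a)]

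For 20% at 2 years, λ = −ln(0.8)/2 = 0.1116. With a = 0.33 and b = 5.03, crude = 1 − (0.9639 − 0.5705)/(0.1116 × 4.7) = 25.0%.

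| Assumed 2-year incidence | Crude, July 2017 | 3-year incidence | 5-year incidence |
|---|---|---|---|
| 10% | 12.9% | 14.6% | 23.2% |
| 20% | 25.0% | 28.4% | 42.8% |
| 30% | 36.2% | 41.4% | 59.0% |

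In the 20% row the crude figure equals the incidence at about −ln(0.75)/0.1116 ≈ 2.6 years, a time nobody chose.

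**Dependence on accrual.** Keep λ = 0.1116 and the 0.33-year gap, but stretch accrual to the 5.9 years the revision avoided (b = 6.23). Crude = 1 − (0.9639 − 0.4990)/(0.1116 × 5.9) = 29.4%. The same toxicity would be reported as 25.0% or 29.4% according to enrolment speed.

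**Other event timings.** If late events start about 0.38 years after randomization and reach 20% at 5 years, the crude figure is 10.3% to 11.9%, against a 2-year incidence of 7.5% to 9.8%. The ranges cover competing hazards from zero up to the PFS hazards in Section 13.5. If instead all late events arise within 2 years and total 20%, the crude figure is about 16.5%.

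**Final analysis.** Section 13.6.4 places it about 2.7 years after accrual ends, so e runs from 2.7 to 7.4 years. With λ = 0.1116, crude = 1 − (0.7399 − 0.4380)/(0.1116 × 4.7) = 42.4%, close to the 5-year 42.8%.

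**Comparison of arms.** Staggered entry is shared by both randomized arms. Unequal survival is not. With the PFS hazards (0.37 in year 1, then 0.15) as an upper-end competing hazard, a control-arm late incidence of 20% at 5 years and a hazard ratio of 0.65 on the competing hazard only, the crude rates are 11.9% and 13.9% although the late-event hazard is identical.

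**The case against.** The initial report is timed to the end of concurrent therapy, and its emphasis is on compliance and adverse events. It promises no 2-, 3- or 5-year late rate. Acute events during concurrent treatment are fully observed by then, apart from maintenance in a handful of late entrants. Adverse events are tabulated again at the final analysis, when minimum potential follow-up is about 2.7 years, and unless the trial stops early the phase III decision rests on the PFS test at that point. Part of late function is already measured at fixed times: PSS-HN, the FACT-H&N subscale and XeQOLS at 3, 12 and 24 months after radiotherapy in consenting patients. Appendix I schedules no follow-up audiogram or thyroid test, so onset dates for those events would be clinical and imprecise.

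Most of this stands and limits the point. It does not remove it: adverse events continue to be collected in follow-up, everything recorded enters one proportion, and the same undefined horizon carries into the final report.

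A reader might go further and infer that late toxicity is systematically understated. The documents do not support that. The plan does not stop counting at any fixed time, so patients followed for 3 to 5 years contribute late events, and under a constant hazard the crude figure exceeds the 2-year incidence. It falls short only against horizons of about 3 years and beyond, or where events cluster early. Nor is Fisher's test shown to be biased: that would need a survival difference between arms.

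**Conclusion.** The point holds as a matter of definition. For late events, the planned proportion and its interval at July 2017 correspond to no stated time and vary with the accrual pattern. In the illustration, a hazard giving 20% at 2 years is reported as 25.0%, against 28.4% at 3 years and 42.8% at 5 years. This rests on uniform accrual, a constant late-event hazard and no deaths; the documents supply no late-event rate, and the direction of the discrepancy depends on the horizon and on when events arise.

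Acute toxicity, the sample size and the PFS decision rule are untouched or nearly so. At the final analysis the crude figure comes close to the 5-year value in the illustration, but only because mean potential follow-up happens to be about (2.7 + 7.4)/2 ≈ 5 years. This is a cheap improvement, not a flaw that threatens the trial.

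**What to change.** In Sections 13.6 and 13.6.3, split adverse-event reporting in two.

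- **Early window.** Keep the binomial estimate, 95% interval and Fisher's exact test for a fixed period that every analysed patient has completed at the data cut, for example from first dose to a set day after radiotherapy.
- **Later events.** Report cumulative incidence at fixed times, for example 1 and 2 years, with death as a competing risk and censoring at the last adverse-event assessment. Compare arms with the cause-specific log-rank test already specified in Section 13.6; because it compares hazards among patients still at risk, it also addresses unequal survival.

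Apply the same split to the tabulation in Section 13.6.4. The cost is SAP wording and modest programming, using assessment dates that follow-up already provides. The downside is two toxicity tables in place of one and wider intervals for late events.
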